### **Recruitment**

Individuals will be recruited from the Atlanta VA Rehab R&D Subject Registry (IRB00000159) based on the inclusion and exclusion criteria. The Subject Registry study staff will query the database of all patients meeting the inclusion and exclusion criteria who have consented to be contacted for research purposes and will print out their contact information. The Principal Investigator, or his research colleagues, will contact these individuals and will summarize the study procedures. If the potential participant is interested, we will mail them a copy of the informed consent and will

schedule an orientation session that describes the study goals and provides an opportunity to go over the informed consent.

In order to decrease burden of the potential recruitment pool of participants, cognitive, motor, and physical function measurements will be shared between this study Effects of Acute Exercise on Functional Magnetic Resonance Spectroscopy Measures of GABA in Aging and Chronic Stroke (IRB00001334) and Graded Intensity Aerobic Exercise to Improve Cerebrovascular Function and Performance in Aged Veterans (IRB00106626) as all studies administer the same assessments.

Healthy subjects will also be recruited via the Emory University Alzheimer Disease Research Center (ADRC) Registry. Written permission from all patients is recorded on a signed informed consent form before inclusion in the ADRC Registry. This consent requires that the patients be willing to complete detailed histories, undergo comprehensive neurological and neuropsychological evaluations on an annual basis; submit blood for ascertainment of genetic information and establishment of lymphoblastoid cell lines; and agree to be contacted regarding participation in research projects of Emory investigators.

CDW/VINCI data will be used to identify potential research participants. Veterans who are age 65 or older and who live within 20 miles of the Atlanta VA Health Care System will be identified and contacted via mail and then subsequently by phone. Addresses and phone numbers will be used for recruitment only and the information will be verified as current and accurate in CPRS prior to use.

Additionally, participants may be recruited from word of mouth, newspaper advertisement, and study flyer distribution within the Atlanta VA Health Care System and surrounding community.

Individuals will be provided a copy of the informed consent and will be scheduled for an orientation session that describes the study goals and provides an opportunity to go over the informed consent. The PI/Co-Investigator or their trained and qualified colleagues will go over and describe the consent in a private office of the PI/Coinvestigator.

## **7. Statistical Analysis:**

### **Statistical Analysis for Specific Aim 1**

Specific Aim 1 is to determine whether there will be a statistically significant difference in the cerebral perfusion data between the two groups (Spin and Control) following the intervention. We will assess the perfusion values jointly using a linear mixed-effects model to determine whether the mean change in perfusion between the groups is significantly different. For the model the fixed effect will be group (Spin vs Control) and the random effect will be time (Pre vs Post). We expect that modeling the outcomes jointly will increase the statistical power. This model will enable us to estimate the

overall effects of time and the interventions, and most importantly, how the effects of the interventions differ with time. Additional analyses will use multiple regressions to describe the effect of participant demographics such as gender, race, age, hypertensive status as well as MoCA score. A false discovery rate (FDR) of  $q = 0.05$  will be calculated and used to correct for multiple tests and effect sizes will be computed.

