### **Statistical Analysis for Specific Aim 2**

Specific Aim 2 is to determine the impact of an aerobic intervention on CVR. Similar to Aim 1, we will test each BOLD change value jointly using a linear mixed-effects model to determine whether the mean change of the groups is significantly different across the time points (Pre and Post). Fixed effect will be group (Spin vs Control) and the random effect will be time (Pre vs Post). Additional analyses will use multiple regressions to describe the effect by participant demographics (gender, race, age, and hypertensive status) or by MoCA score. An FDR of  $q = 0.05$  will be calculated and used to correct for multiple test and effect sizes will be computed.

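### Aims 1 and 2 compare mean change between arms without adjusting for the baseline scan, which costs precision by an amount that depends on a pre-post correlation the plan does not give

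*Combined protocol and SAP*

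**What the plan says.** The Aim 1 analysis (section 7, Statistical Analysis for Specific Aim 1) uses a linear mixed-effects model to "determine whether the mean change in perfusion between the groups is significantly different". The terms are given as follows: "For the model the fixed effect will be group (Spin vs Control) and the random effect will be time (Pre vs Post"). The model is also meant to show "how the effects of the interventions differ with time", which points to a group-by-time contrast.

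The Aim 2 analysis is parallel. It will "determine whether the mean change of the groups is significantly different across the time points (Pre and Post"), with the same terms: "Fixed effect will be group (Spin vs Control) and the random effect will be time (Pre vs Post").

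In neither section is the baseline value of perfusion or CVR a covariate, and neither says that the arms share one baseline mean. The additional regressions cover "participant demographics such as gender, race, age, hypertensive status as well as MoCA score" for Aim 1, and "gender, race, age, and hypertensive status) or by MoCA score" for Aim 2. Baseline perfusion and baseline CVR are on neither list. The section on FMRI Tasks has participants scanned before and after the 12 weeks, so the pre value will be available.

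**The concern.** A change score subtracts the whole baseline value, although pre and post measurements correlate below 1. Part of what is subtracted is noise, and it passes into the treatment contrast. Adjusting for baseline subtracts only the part that predicts the post value. In a randomised comparison it estimates the same effect with a smaller standard error.

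Two things are at stake. The first is precision: the trial plans for 44 per arm, and Power Analysis and Sample Size says it is powered mainly on Aim 1. The second is chance imbalance. If the arms happen to differ at baseline, a change-score estimate is shifted in that particular trial, and adjustment removes the shift.

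**Working it through.** **Inputs.** From Power Analysis and Sample Size: 44 per group; alpha 0.0261 after FDR correction; d = 0.64 for 0.80 power. That d is the only between-group effect size for which the plan states a power. It is given for behavioural data, and I take it here on the change scale. Sidedness is not stated, so I assume two-sided. The two arms are Spin and Control, as in the analysis sections. No pre-post correlation, reliability or SD of change is given for perfusion or CVR, so ρ is assumed and shown from 0.3 to 0.9.

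**Step 1: the plan's own figure.** Normal approximation: power = Φ(d√(n/2) − z). Here 0.64 × √22 = 3.002 and z at two-sided 0.0261 is 2.225, so power = Φ(0.777) = 0.78. The noncentral t gives 0.77. This is close to the stated 0.80. The between-group sentence prints alpha as .05 (FDR corrected); two-sided 0.05 would give 0.85 (normal) or 0.84 (t).

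**Step 2: what the planned contrast equals.** The listed terms contain no subject effect and no group-by-time term, so taken literally they do not define a contrast in change. The natural reading adds both. With two time points, complete pairs and baseline means free to differ by arm, the group-by-time coefficient is the difference in mean change. A simulation (44 per arm, 100 runs each at ρ = 0.3 and 0.8) confirmed this: the mixed-model and change-score estimates differed by less than 1e-14.

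**Step 3: variances.** Let σ be the common pre and post SD and n the number per arm.

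- Change score: 2σ²(1−ρ) × 2/n
- Baseline-adjusted: σ²(1−ρ²) × 2/n
- Ratio, adjusted to change: (1−ρ²) / [2(1−ρ)] = (1+ρ)/2
- Reduction: (1−ρ)/2

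**Step 4: size.** The effect in raw units is unchanged, so the standardised effect after adjustment is 0.64/√((1+ρ)/2). Power is by noncentral t, 44 per arm, two-sided alpha 0.0261. The unadjusted value is 0.77 throughout.

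| Assumed ρ | Variance reduction | Adjusted n per arm with the precision of 44 unadjusted | Standardised effect after adjustment | Power after adjustment |
|---|---|---|---|---|
| 0.3 | 35% | 28.6 | 0.79 | 0.93 |
| 0.5 | 25% | 33.0 | 0.74 | 0.88 |
| 0.7 | 15% | 37.4 | 0.69 | 0.84 |
| 0.8 | 10% | 39.6 | 0.67 | 0.81 |
| 0.9 | 5% | 41.8 | 0.66 | 0.79 |

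**Step 5: chance imbalance.** If the arms differ by δ at baseline, the change-score estimate shifts by (1−ρ)δ, in the direction opposite to δ. For δ = 0.3 SD this is 0.15 SD at ρ = 0.5 and 0.06 SD at ρ = 0.8. At ρ = 0.5 the standard error is √(2 × 0.5 × 2/44) = 0.213 SD, so the shift is about 0.7 of a standard error. The standard error of a baseline difference is √(2/44) = 0.213 SD, so an imbalance of 0.3 SD or more in either direction arises by chance in about 16% of trials.

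**The case against.** **The plan does use the pre scan.** It enters as a repeated outcome, and a mixed model with a common baseline mean would recover nearly all the gain; the text neither adopts nor excludes that model. This stands, and a reader should not infer that the baseline is ignored. But the gain arises only if the constraint or the covariate is specified, and neither is.

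**The change-score identity needs inferred terms and complete pairs.** This also stands. Participant selection expects 15-20% dropout. A likelihood-based mixed model keeps participants who have only a pre scan, so it would no longer match the completers' change scores exactly. A regression of post on pre would drop those participants, and run one ROI at a time it would also lose the joint modelling that the plan expects to raise power. This bears on the choice of fix more than on the concern.

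**Allocation is described as pseudorandomised, with no method given.** If it is not effectively random, adjusted and change-score analyses can target different quantities, and forcing equal baseline means could bias the result. The claim that both estimate the same effect is therefore conditional.

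**The plan puts Aim 1 power close to 1, so precision may seem to spare.** That figure takes d = 2.740, a cross-sectional difference between active and sedentary adults in a small sample (n=10), as the change within the Spin group. It is not a between-arm effect. The d = 0.5 that the plan links to 0.80 power gives 0.53 as a two-group t test at 44 per arm and alpha 0.0261.

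**Demographic covariates.** A reader might infer that age, gender and hypertensive status must move into the primary model. The documents give nothing from which to show a gain, and these variables already appear in the additional regressions.

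**Conclusion.** The concern holds as a conditional loss of precision. For both aims the planned contrast, on its natural reading, has a larger variance than a baseline-adjusted one whenever ρ is below 1, and adjustment would reduce it by (1−ρ)/2. This rests on equal pre and post SDs, complete pairs, the inferred subject and group-by-time terms, and allocation that is effectively random. The power figures also rest on d = 0.64 applying to change in perfusion or CVR.

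Two stronger readings are tempting and not supported. One is that the plan forfeits a known 10-35% of variance. That range is only (1−ρ)/2 for ρ from 0.8 down to 0.3; the documents supply no ρ, and at 0.9 the gain is 5%. The other is that the change-score comparison is invalid or biased. Under randomisation it is unbiased on average and its type I error is sound; the bias in Step 5 is conditional on a chance imbalance having occurred.

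**What to change.** For perfusion and for CVR, state as the primary analysis a longitudinal mixed model with a subject effect, time, group-by-time, and one common baseline mean for the randomised arms. The group-by-time coefficient is the treatment effect. This keeps participants with only a pre scan, can keep the ROIs modelled jointly, and also settles the missing subject and group-by-time terms. With complete pairs, the equivalent is to regress the post value on arm with the same ROI's pre value as covariate.

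State how the pseudorandomisation works. If allocation is not effectively random, use the pre value as a covariate instead of forcing equal baseline means, and report the change-score result as a sensitivity analysis. Adding age, gender and hypertensive status to the primary model is optional; if they are wanted, name them in advance.

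The cost is SAP wording only, with no new data. Under effectively random allocation, type I error control is not weakened.

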### **Behavioral and Self-Report Data**

The analysis plan for behavioral performance will include the following dependent variables: semantic fluency performance and the motor tests, MOCA, and VO2 submax, and each self-report outcome. Paired t-tests will be performed to test for a pre- to post effect on fluency and motor skills. Similarly, subscale scores and total scores will be evaluated pre to post intervention for each self-report measure. Spearman’s correlations ( $r_s$ ) will be used to correlate behavioral performance to primary outcomes and a mixed regression will be used to assess the influence of session (pre and post) on outcomes.

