### **Power Analysis and Sample Size**

For Aim 1, we used preliminary data comparing older active adults to older sedentary adults. Effect size for difference in inferior frontal perfusion for a small sample ( $n=10$ ) was  $d=2.740$ . If this effect size is taken as an estimate of the effect size for change in the Spin group with  $n=44$  and  $\alpha$  FDR-corrected to 0.0261, then power approaches 1.00. A more conservative estimated change in perfusion being half the effect, with the standard deviation remaining constant, would produce an effect size of 1.370. With the same  $n$  and  $\alpha$  as above, the power still approaches 1.00. The required effect size to achieve a power of 0.80 would be  $d=0.5$ , which would seem quite achievable given our preliminary data. Hence, the power should be more than adequate and seems plausible based on what we know. Because we want to maintain sensitivity at this level, the study is powered mainly to this Aim, while power for Aims 2 and 3 is more than adequate. For

example, for Aim 3, with  $\alpha < .05$ , minimum power of 0.80 and 88 subjects, we have the power to detect an increase in  $R^2$  as small as 0.111 in each ROI. We have detected significant correlations between BOLD response in M1 and IFG with smaller sample sizes (n=36 and n=41, respectively). Accounting for much less than 11% of the variance in criterion variables with the predictors would be too little variance to provide information useful for the design of future clinical trials. Hence, we should have the power to detect effects large enough to impact future clinical trials.

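### Aims 1 and 2 list only group (fixed) and time (random), so no term in the model tests the between-group difference in change that both aims promise

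*Combined protocol and SAP*

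**What the plan says.** Statistical Analysis for Specific Aim 1 gives the purpose of the model as "to determine whether the mean change in perfusion between the groups is significantly different". It expects the model to estimate "overall effects of time and the interventions, and most importantly, how the effects of the interventions differ with time". Between these two statements comes the only specification of terms: "For the model the fixed effect will be group (Spin vs Control) and the random effect will be time (Pre vs Post").

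Statistical Analysis for Specific Aim 2 sets a parallel target for CVR, to "determine whether the mean change of the groups is significantly different across the time points (Pre and Post"), and lists the same terms: "Fixed effect will be group (Spin vs Control) and the random effect will be time (Pre vs Post").

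No other section supplies the missing terms. Under Behavioral and Self-Report Data, "a mixed regression will be used to assess the influence of session (pre and post) on outcomes", which concerns session and not group × session. The only interaction written out in Section 7 is perfusion × CVR in the Aim 3 regression. Under Power Analysis and Sample Size, after the Aim 1 calculation, the plan says "the study is powered mainly to this Aim".

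**The concern.** The Aim 1 text promises three results: the overall time effect, the overall intervention effect and, as the most important, how the intervention effect differs with time. The third is group × time. A model with group as its only fixed effect gives the second result alone. A random time effect contributes a variance component, not a contrast between arms, and participant-level random time slopes would still add no fixed group × time term.

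This is the main test of two of the three aims, including the one the study is mainly powered for. An analyst who fits the listed terms tests a quantity that answers neither aim. An analyst who follows the stated purpose has to add terms that the plan does not list, so the model behind the main test is not fixed in advance.

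**Working it through.** **1. What the listed fixed effect estimates.** Let D_pre and D_post be the Spin minus Control differences at each visit, and let Δ = D_post − D_pre be the target. With group as the only fixed effect, the coefficient is

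β = w·D_pre + (1 − w)·D_post = D_pre + (1 − w)·Δ.

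The visit weights sum to 1, whereas Δ needs weights −1 and +1. No choice of w gives Δ.

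- Balanced data, equal variances, participant intercept: w = 1/2, so β = D_pre + Δ/2.
- Uncorrelated participant time slope, assumed variances 0.7 (intercept), 0.3 (slope), 0.3 (residual): visit variances are 1.0 and 1.3 with covariance 0.7. The weights are proportional to 1.3 − 0.7 = 0.6 (pre) and 1.0 − 0.7 = 0.3 (post), so 33% of Δ enters β.
- Pre-only scans kept, share p with both scans: post weight = [p/(1+ρ)] / [2p/(1+ρ) + (1−p)]. At the 15–20% dropout in Section 6 and ρ from 0.5 to 0.85, this is 0.43–0.44 (p = 0.85) and 0.41–0.42 (p = 0.80).

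**2. The plan's own between-group figure.** Power Analysis and Sample Size gives d = 0.64 for power 0.80 with 44 per group (semantic fluency). Two-sided noncentral t, df = 86, noncentrality 0.64·√(44/2) = 3.00: power is 0.768 at alpha 0.0261 (0.781 by normal approximation) and 0.843 at 0.05. The figure is approximately reproduced, and it describes a test of difference in change.

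**3. Power of the averaged coefficient.** Inputs: n = 44 per arm; alpha 0.05 and the plan's 0.0261; d = 0.64; and d = 1.37, from the plan's statement that "A more conservative estimated change in perfusion being half the effect, with the standard deviation remaining constant, would produce an effect size of 1.370". Here d is the between-group difference in change in change-SD units. Both values are borrowed: 0.64 is behavioural, and 1.37 is half of an active-versus-sedentary difference. Assumptions not in the documents: ρ = 0.5, 0.7 or 0.85, unit SD at both visits, complete data, one outcome per scan, no baseline difference, two-sided tests and a participant random intercept.

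- Group × time: SE = √(4(1−ρ)/n), noncentrality d·√(n/2).
- Averaged coefficient: effect ½·d·√(2(1−ρ)), SE = √((1+ρ)/n).

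Example with ρ = 0.7, d = 0.64: Δ = 0.64·√0.6 = 0.496; half is 0.248; SE = √(1.7/44) = 0.197; noncentrality 1.26; power 24% at alpha 0.05.

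| d | alpha | group × time | averaged, ρ = 0.5 | ρ = 0.7 | ρ = 0.85 |
|---|---|---|---|---|---|
| 0.604 | 0.05 | 80% | 37% | 22% | 12.5% |
| 0.64 | 0.05 | 84% | 40% | 24% | 13.5% |
| 1.37 | 0.05 | >99% | 96% | 76% | 44% |
| 0.64 | 0.0261 | 77% | 30% | 16% | 8.5% |
| 1.37 | 0.0261 | >99% | 92% | 67% | 34% |

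Simulation at alpha 0.05 (20,000 trials per cell) agrees: 0.399, 0.241, 0.135 for d = 0.64 and 0.956, 0.764, 0.445 for d = 1.37.

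**4. Baseline imbalance.** D_pre enters β in full. In simulation (4,000 trials per setting, alpha 0.0261) with no intervention effect and an assumed 0.3 SD baseline difference, the averaged coefficient rejected in 22–27% of trials for ρ from 0.5 to 0.8. Group × time stayed at 2.6–2.9%.

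**5. Strictly literal reading, with time the only random factor.** Two scans of one person are then treated as independent. The standard error used is too small by a factor √(1+ρ), and type I error is 2·(1 − Φ(1.96/√(1+ρ))) = 11%, 13% and 15% at nominal 5%. Rejection rates at alpha 0.05 are about 55%, 41% and 29% for d = 0.64, and 98%, 88% and 65% for d = 1.37. They are inflated by that type I error, so they are not valid power.

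**The case against.** The strongest reply is that the target is already fixed. Both aims name the difference in mean change, and the Aim 1 text singles out how the intervention effect varies with time. On that view fixed and random are loose labels for a between-participant and a repeated factor, the right hypothesis would be tested, and the defect is incomplete notation with no loss of power. This reading is plausible and part of it stands: the intent is clear. But the only explicit list of terms contradicts that intent, and an analyst must override it to honour the purpose.

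A second reply is that the outcome could be the change score, which would make group the right term. Time (pre vs post) could not then be in the model. The BOLD change value in Aim 2 is most naturally the CO2 response at each session.

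The third reply concerns size, and it stands as a limit on the figures. The table adds a participant intercept, which the plan does not list, to the listed fixed effect, so it describes neither the strictly literal model nor the intended one. The result for 1.37 also depends on scale: read in visit-SD rather than change-SD units, the averaged coefficient has about 96%, 93% and 91% power at alpha 0.05. The plan itself uses 1.37 as an effect size for change, so change-SD units are defensible, but the loss at that effect is not firmly known. None of this turns the listed coefficient into the difference in change.

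**Conclusion.** The concern holds as a contradiction within the plan: the terms listed for Aims 1 and 2 cannot estimate the quantity that both aims say they test. That is structural and needs no assumption about correlation or effect size. In the balanced case half of the intended effect reaches the coefficient, mixed with the whole baseline difference.

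The loss of power is conditional. It is zero if the analyst fits the intended group × time model. Otherwise, under the assumptions stated in the working, it is large at moderate effects (84% falls to between 13.5% and 40% for d = 0.64 at alpha 0.05) and smaller at very large ones. Because this is the main test for the aim that drives the sample size, it must be corrected before analysis.

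**What to change.** In the Aim 1 and Aim 2 analysis sections, replace the model sentence with: *Fixed effects are group (Spin vs Control), time (pre vs post, categorical) and group × time, with a participant random intercept. The main test is the group × time coefficient.*

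If regions of interest are modelled jointly, add region as a within-participant fixed factor with participant-by-visit and participant-by-region random effects, and say how the pooled test relates to the planned FDR correction. Baseline-adjusted ANCOVA of the post value is an acceptable pre-specified alternative, but this correction does not require it.

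The cost is SAP wording only: no new data and no further participants.
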